2.2 Study Disease and correlative studies background

The prothrombotic state associated with malignant disease has been a recognized entity since the 1800's. Almost 1 in 5 cases of venous thromboembolism (VTE) are thought to be related to cancer, and thrombosis is the second leading cause of mortality in cancer populations.³⁵ The risk of thrombosis attributed to the malignant state is not uniform across all histological diagnoses. There is a 10-fold greater rate of VTE among patients suffering from ovarian, brain, and pancreatic cancers compared to those with other histologies.³⁶ Randomized clinical trials have demonstrated a small absolute risk reduction in VTE with primary thromboprophylaxis of low molecular weight heparins. The absolute risk of VTE in these unselected cohorts is low (3-5%) and thus the benefit of daily injection and potential risk for bleeding has tempered enthusiasm for non-targeted thromboprophylaxis approaches. Different models and biomarkers are under investigation to identify those patients who are highest risk of developing thrombosis and thus would benefit the most from primary thromboprophylaxis. Khorana and colleagues developed and validated a scoring model that identified higher risk patients based on elevated platelet count, white blood cell count, body-mass index, and anemia.³⁷

Pathologic changes in microparticle populations contribute to the hypercoagulability associated with various disease states, including malignancy. Microparticles are vesicular structures measuring less than 1 µm in size and are derived from a number of cells within the vascular compartment including leukocytes, platelets, red blood cells, and endothelial cells.³⁸ Some microparticles are considered procoagulant due to the exposure of negatively charged phospholipids on the external membrane leaflet for the support of thrombin generation.^{39,40} Subpopulations of microparticles also express tissue factor, the in vivo initiator of blood coagulation.^{41,42} Circulating tissue factor-bearing microparticles augment thrombus formation in animal models⁴³ and tumor-derived microparticles accumulate at the site of vascular injury.⁴⁴ Our group previously demonstrated that tissue factor bearing microparticles are elevated in cancer patients diagnosed with VTE and appear to be derived from the underlying tumor.⁴⁵ The association between tissue factor bearing microparticles and VTE has been described by several groups as well, including in a mouse model of vascular injury.^{44,46} Notably, in our study the 1 year cumulative incidence of thrombosis in cancer patients with increased tissue factor bearing microparticles was 34.8% versus 0% in those without detectable tissue factor bearing microparticles.⁴⁵ We recently completed a randomized phase II trial of low molecular weight heparin to prevent thrombosis in cancer patients with elevated tissue factor bearing microparticles.⁴⁷ The primary endpoint was the cumulative incidence of VTE at 60 days, as defined by symptomatic VTE or asymptomatic proximal DVT diagnosed by protocol-mandated bilateral lower extremity ultrasound. The overall cumulative incidence of thrombosis across the study was 11.3% at 60 days. The cumulative incidence of thrombosis in the high tissue factor bearing microparticle patients was 27% (N=11) compared with 5% (N=23) in those treated with low molecular weight heparin (P=0.06).

2.3 Rationale

Despite the high incidence and morbidity associated with VTE in cancer patients, primary thromboprophylaxis is not routinely recommended by oncologists largely due to a modest absolute benefit in unselected cancer cohorts and the need for patients to self-administer a daily injection. We previously observed a cumulative incidence of VTE of 11.3% at 60 days in patients with advanced non-small lung cancer, pancreatic cancer, and colorectal cancer.⁴⁷

Protein disulfide isomerase released by platelets and endothelial cells regulates both platelet accumulation and fibrin generation in animal models. Quercetin and related glucosides were recently discovered to be potent inhibitors of extracellular PDI activity in vitro and in vivo.² Antithrombotic properties of quercetin have been described in humans and we observed that the oral administration of isoquercetin results in PDI-inhibitory activity in human plasma. Fortuitously, isoquercetin is widely available flavonoid nutritional supplement. Based on the safety profile and evident antithrombotic properties of isoquercetin, we aim to evaluate isoquercetin as an anticoagulant in cancer patients in a combined phase II/III clinical trial.

3 PARTICIPANT SELECTION

Laboratory tests required for eligibility must be completed within 15 days prior to study entry

3.1 Eligibility Criteria

Participants must meet the following criteria on screening examination to be eligible to participate in phase 2 and 3 of the study:

3.1.1 Participants must have histologically confirmed malignancy that is metastatic or currently unresectable.

Eligible malignancies include:

- Adenocarcinoma of the pancreas (currently unresectable or metastatic)
- Colorectal (stage IV)
- Non-small cell lung cancer (currently unresectable stage III or stage IV)
- 3.1.2 Receiving or scheduled to receive first or second line chemotherapy (within 30 days of registration)
- 3.1.3 Minimum age 18 years. Because limited dosing or adverse event data are currently available on the use of isoquercetin in participants <18 years of age, children are excluded from this study but will be eligible for future pediatric isoquercetin trials.
- 3.1.4 Life expectancy of greater than 4 months.
- 3.1.5 ECOG performance status ≤ 2 (see Appendix B).
- 3.1.6 Patient must be able to swallow capsules (phase III only)
- 3.1.7 Participants must have preserved organ and marrow function as defined below:

Absolute neutrophil count \geq 1,000/mcL

CONFIDENTIAL This document is confidential. Do not disclose or use except as authorized. $\begin{array}{l} \mbox{Platelets} \geq 90,000/mcL\\ \mbox{PT and } \mbox{PTT} \leq 1.5 \ x \ institutional \ upper \ limit \ of \ normal\\ \mbox{Total bilirubin} < 2.0 \ mg/dl\\ \mbox{AST (SGOT)/ALT (SGPT)} \leq 2.5 \ X \ institutional \ upper \ limit \ of \ normal\\ \mbox{Creatinine} < 2.0 \ mg/dl \end{array}$

- 3.1.8 The effects of isoquercetin on the developing human fetus are unknown. For this reason, women of child-bearing potential and men must agree to use adequate contraception (hormonal or barrier method of birth control; abstinence) prior to study entry and for the duration of study participation. Should a woman become pregnant or suspect she is pregnant while participating in this study, she should inform her treating physician immediately.
- 3.1.9 Ability to understand and the willingness to sign a written informed consent document.

3.2 Exclusion Criteria

Participants who exhibit any of the following conditions at screening will not be eligible for admission into phase 2 or 3 of the study.

- 3.2.1 Participants may not be concurrently receiving any other study agents.
- 3.2.2 Participants with known brain metastases should be excluded from this clinical trial because of their poor prognosis and because they often develop progressive neurologic dysfunction that would confound the evaluation of neurologic and other adverse events.
- 3.2.3 Prior history of documented venous thromboembolic event within the last 2 years (excluding central line associated events whereby patients completed anticoagulation).
- 3.2.4 Active bleeding or high risk for bleeding (e.g. known acute gastrointestinal ulcer)
- 3.2.5 History of significant hemorrhage (requiring hospitalization or transfusion) outside of a surgical setting within the last 24 months
- 3.2.6 Familial bleeding diathesis
- 3.2.7 Known diagnosis of disseminated intravascular coagulation (DIC)
- 3.2.8 Currently receiving anticoagulant therapy

- 3.2.9 Current daily use of aspirin (>81mg daily), Clopidogrel (Plavix), cilostazol (Pletal), aspirin-dipyridamole (Aggrenox) (within 10 days) or considered to use regular use of higher doses of non-steroidal anti-inflammatory agents as determined by the treating physician (e.g ibuprofen > 800 mg daily or equivalent).
- 3.2.10 Uncontrolled intercurrent illness including, but not limited to ongoing or active infection, symptomatic congestive heart failure, unstable angina pectoris, cardiac arrhythmia, or psychiatric illness/social situations that would limit compliance with study requirements.
- 3.2.11 Known intolerance of niacin or ascorbic acid (including known G6PD deficiency)
- 3.2.12 Pregnant women are excluded from this study because isoquercetin is a PDI inhibitor with the potential for teratogenic or abortifacient effects. Because there is an unknown but potential risk of adverse events in nursing infants secondary to treatment of the mother with isoquercetin, breastfeeding should be discontinued if the mother is treated with isoquercetin. These potential risks may also apply to other agents used in this study.

3.3 Inclusion of Women, Minorities and Other Underrepresented Populations

The study is open to any individual who has an advanced malignancy without discrimination based on race or gender. We do not anticipate that inclusion or exclusion criteria will negatively affect recruitment or retention of underrepresented minorities.

4 REGISTRATION PROCEDURES

4.1 General Guidelines for DF/HCC and DF/PCC Institutions

Institutions will register eligible participants with the DF/HCC Quality Assurance Office for Clinical Trials (QACT) central registration system. Registration must occur prior to the initiation of therapy. Any participant not registered to the protocol before treatment begins will be considered ineligible and registration will be denied.

An investigator will confirm eligibility criteria and a member of the study team will complete the QACT protocol specific eligibility checklist.

Following registration, participants may begin protocol treatment. Issues that would cause treatment delays should be discussed with the Overall Principal Investigator (PI). If a participant does not receive protocol therapy following registration, the participant's registration on the study may be cancelled. . Notify the QACT Registrar of registration cancellations as soon as possible.

4.2 Registration Process for DF/HCC and DF/PCC Institutions

DF/HCC Standard Operating Procedure for Human Subject Research Titled *Subject Protocol Registration* (SOP #: REGIST-101) must be followed.

4.3 General Guidelines for Other Participating Institutions

Eligible participants will be entered on study centrally at BIDMC by the Study Coordinator. All sites should call the Study Coordinator at [contact] to verify treatment availability and eligibility.

Following registration, participants should begin protocol treatment within 72 hours or as soon as possible. Issues that would cause treatment delays should be discussed with the Principal Investigator. If a participant does not receive protocol therapy following registration, the participant's protocol status must be changed. The Study Coordinator should be notified of participant status changes as soon as possible.

4.4 Registration Process for Other Participating Institutions

To register a participant, the following documents should be completed by the research nurse or data manager and faxed the Study Team:

to

- Copy of all eligibility and screening documents
- Signed participant consent form

- HIPAA authorization form (if applicable)
- Eligibility Checklist

The research nurse or data manager at the participating site will then call **and the second of** e-mail **and the study** Coordinator to verify eligibility. To complete the registration process, the Coordinator will follow DF/HCC Standard Operating Procedure for Human Subject Research Titled *Subject Protocol Registration* (SOP #: REGIST-101) and register the participant on the protocol. The coordinator will fax or email the participant study number, and if applicable the dose treatment level, to the participating site. The coordinator will also call the research nurse or data manager at the participating site and verbally confirm registration

5 TREATMENT PLAN

Treatment will be administered on an outpatient basis. Expected toxicities and potential risks as well as dose modifications for isoquercetin are described in Section 6 (Expected Toxicities and Dosing Delays/Dose Modification).

Phase	Agent*	Isoquercetin Dose	Route	Schedule	Cycle
Phase II	Isoquercetin (IQC- 950AN) 250mg	Cohort A: 500 mg or Cohort B: 1000 mg	Oral capsules	Cohort A: 2 capsules once daily Cohort B: 4 capsules once daily	28 days
Phase III	Isoquercetin (IQC- 950AN) or Placebo	Cohort C: TBD or Cohort D: Placebo	Oral capsules	Once daily (TBD)	28 days

*All capsules (placebo and isoquercetin) include ascorbic acid 62 mg and niacin 5 mg.

Phase II

Cohort A: Patients will receive isoquercetin 500 mg once daily (2 capsules). Continued enrollment into the dosing cohort will be based on the safety evaluation of the initial 5 patients. If there are ≥ 1 grade 3 or 4 toxicity (possibly, probably or definitely related to isoquercetin), then decision to enroll an additional cohort of 25 patients will be based on DSMC recommendations. If there are ≥ 3 grade 3 or 4 adverse events (possibly, probably or definitely related to isoquercetin), the decision to proceed with enrollment into cohort B will be based on PSMC.

Cohort B: Patients will receive isoquercetin 1000 mg once daily (4 capsules). Similar to cohort A, continued enrollment will be based on the absence of attributable significant toxicities.

For both cohorts A and B, lower extremity ultrasound will be performed at end of treatment visit. Baseline D-dimer and correlative labs will be drawn at Day 1 and at end of treatment visit. Patients will be followed for survival after completion of end of treatment visit.

Phase III

Following the completion of the phase II portion, enrolled patients will be randomized 1:1 to Arm C (isoquercetin) or Arm D (placebo). The dose for Arm C will be determined after evaluation of the Phase II portion of the trial. The protocol will be amended when the decision is made whether to proceed to Phase III and what dose to use for Arm C. The study will be double-blinded to treatment arm. Lower extremity ultrasound will be performed at end of treatment. Baseline D-dimer and correlative labs will be drawn at Day 1 and at end of treatment. Patients will be followed for survival after completion of end of treatment assessment.

At BIDMC, optional blood draw will be performed at time 0 and 4 hours following the first dose of study drug. Non-collection of the optional blood draw will be permitted if patients ultimately decide not to stay for the 4 hour collection.

NOTE: all capsules also have ascorbic acid and niacin to improve stability and bioavailability of isoquercetin.

5.1 Pre-treatment Criteria

- 5.1.1 Cycle 1, Day 1 (see Appendix C for C1D1 checklist)
 - Laboratory assessments recorded within 15 days of signing consent may be used to determine eligibility and does not have to be repeated (except complete blood count)
 - Absolute neutrophil count > 1,000/mcL
 - Platelet count > 90, 000 / μ l
 - Patients must be able to tolerate PO capsules (phase III only)
 - 5.1.2 Cycle 2, Day 1 (Day 29) (see Appendix C for C2 D1 checklist)
 - Adequate platelet count (see section 6.3)
 - Non-heme toxicities possibly related to isoquercetin must return to grade 2 or less

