5.2 Agent Administration

5.2.1 Isoquercetin or placebo

Depending on assigned Cohort during Phase II or randomization in Phase III each capsules will contain 250 mg isoquercetin versus placebo. Isoquercetin will be supplied as oral capsules. Capsules will be consumed once daily (2 or 4 capsules depending on cohort designation). Dose modifications will not be

made. Capsules will be dispensed from the research pharmacy on C1D1 and again on C2D1. The capsules will be packaged as a 30 day supply (to allow for unexpected occurrences such as dropped capsule).

Capsules may be swallowed with or without food. The capsules can be opened and the contents mixed with a small portion of soft acidic food such as apple sauce, puree of carrots, or pumpkin puree (Phase II only). Missed doses must be taken within four hours of scheduled dose. If longer than four hours, or if dose vomited, skip dose. Subjects will keep a drug diary that will be provided to them by the study team. Subjects will be instructed to return any unused drug. The unused returns will be counted by pharmacy and destroyed on-site per policy.

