6.2 Toxicity Management

Hemorrhage

- No modification: CTCAE grade 1
- HOLD: CTCAE grade 2 hemorrhage

Hold isoquercetin until resolution of grade 2 hemorrhage. The maximum number of consecutive days that isoquercetin can be held is 10 days before the participant must be taken off study. A participant may only hold isoquercetin for one ten day period. If a second grade 2 hemorrhage develops the participant must be taken off study.

• **Discontinue:** CTCAE grade 3-4 hemorrhage or otherwise meets criteria for major hemorrhage such as requiring transfusion 2 units PRBC, postoperative interventional radiology, endoscopic or operative intervention or life threatening consequences including spontaneous bleeding at critical site (intracranial, pericardial, retroperitoneal, intraocular, intraspinal)

In cases of suspected isoquercetin toxicity (non-hematologic only):
Grade 2: if toxicity is tolerable to patient, maintain at same dose. If toxicity is intolerable to the patient, then interrupt quercetin until recovery to grade <1
Grade 3 : interrupt until grade <1
Grade 4 : discontinue isoquercetin

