6.3 Dose Modifications/Delays

For non-hematologic toxicity, see section 6.2 for dose delays.

For thrombocytopenia: Grade 3 (platelet count <50,000 /mcl). Hold study drug until grade 2. The maximum amount of time that the study drug can be held without withdrawing the participant from the study is 10 days.

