9 STUDY CALENDAR

Baseline evaluations are to be conducted within 15 days prior to start of protocol therapy.

All assessments must be performed prior to administration of any study medication. All study assessments and medications should be administered within \pm 7 days of the protocol-specified date, unless otherwise noted.

Event/Procedure	Screening/ Pre- treatment visit	Day 1 (C1D1)	Day 29 (C2D1)	Day 56 or End of Study Treatment	Survival Assessment
Day Range	-15 to 0		+ 2 days	+ 5 days	Q6 months
History Assessments	Х				
Informed Consent	Х				
Inclusion/Exclusion Criteria	Х				
Medical History	Х		х	х	
ECOG Performance Status Score	х		х	х	
Concomitant medication review	Х		Х	х	
Treatment allocation ⁶	Х				
Dispense study drug		х	Х		
Drug Diary Collection ³			х	х	
Safety Assessments					
Physical examination including vital signs	Х		х	х	
Height and Weight	Х				
AE/SAE assessment	Х		х	х	
Assessment of signs and symptoms of VTE and bleeding	х		х	х	
Laboratory Tests					
Complete blood count with diff	Х	х	х	Х	
РТ/РТТ	Х				
Creatinine	Х		Х		
AST/ALT	Х		Х		
Total bilirubin	Х				
Urine HCG ⁴	Х				
Correlative plasma samples (all sites) ¹		x		х	
Correlative plasma samples (BIDMC only)		X5		х	
Imaging					
Bilateral lower extremity ultrasound				х	
Quality of Life Survey ²		Х		х	

CONFIDENTIAL This document is confidential. Do not disclose or use except as authorized. ¹Correlative lab instructions (TFMP) provided in Appendix E
²QOL survey provided in Appendix D
³Drug Diary
⁴If applicable
⁵Optional correlative labs to be drawn at time 0 and 4 hours (see section 7.1)
⁶Phase II treatment allocation is by sequential dosing cohort, Phase III allocation is by randomization

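### The Day 29 criterion in Section 5.1.2 and Appendix C sets a looser recovery threshold for related non-heme toxicity than Section 6.2 requires before drug resumes

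*Combined protocol and SAP*

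**What the plan says.** Section 5.1.2, under the pre-treatment criteria, sets two conditions for Day 29. The platelet condition points to its governing rule: "Adequate platelet count (see section 6.3"). The other condition gives its own threshold and no reference: "Non-heme toxicities possibly related to isoquercetin must return to grade 2 or less". The Cycle 2 checklist in Appendix C carries the same sentence.

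Section 6.2 covers suspected isoquercetin toxicity that is non-hematologic:

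- Tolerable grade 2: drug continues at the same dose.
- Intolerable grade 2: "If toxicity is intolerable to the patient, then interrupt quercetin until recovery to grade <1".
- Grade 3: "Grade 3 : interrupt until grade <1".
- Grade 4: drug is discontinued.

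The same section has a separate hemorrhage rule. Grade 2 is held until it resolves, for at most 10 days and once only. Grade 3-4 or otherwise major bleeding means discontinuation.

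Two statements direct the reader to Section 6. Section 5 says "Expected toxicities and potential risks as well as dose modifications for isoquercetin are described in Section 6", and Section 6.3 says "For non-hematologic toxicity, see section 6.2 for dose delays". On supply, Section 5.2.1 says "Capsules will be dispensed from the research pharmacy on C1D1 and again on C2D1".

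**The concern.** Day 29 is when the second supply is handed out, so the line in Section 5.1.2 and the checklist is what a site has in front of it when it decides whether to dispense. That line accepts grade 2. Section 6.2 does not accept grade 2 after a grade 3 event.

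An investigator could complete and sign the Day 29 checklist correctly for a patient whom Section 6.2 still holds. Section 5.2.1 rules out dose modifications, so drug would restart at the full dose. What is at stake is consistent and cautious re-dosing after a related grade 3 toxicity. No efficacy analysis is involved.

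**Working it through.** The plan gives no figure to reproduce here. The check sets the two rules side by side for each state a patient may be in at Day 29.

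Inputs: the Day 29 line (Section 5.1.2 and Appendix C) accepts grade ≤2. Section 6.2 resumes after interruption at grade <1 as printed, or ≤1 if an underline was lost when the PDF was converted to text. The hemorrhage rule is in Section 6.2.

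| Related toxicity, state at Day 29 | Day 29 line | Section 6.2 | Result |
|---|---|---|---|
| Never above grade 2, tolerable | Met | Continue | Agree |
| Grade 3, still grade 3 | Not met | Interrupted | Agree |
| Grade 3, now grade 2 | Met (2 ≤ 2) | Interrupted (2 is neither <1 nor ≤1) | Differ under either sign |
| Grade 3, now grade 1 | Met | Interrupted if <1, may resume if ≤1 | Depends on the sign |
| Grade 3, now grade 0 | Met | May resume | Agree |
| Intolerable grade 2, still grade 2 | Met on the literal wording | Interrupted | Differ only if the line covers toxicities that never exceeded grade 2 |
| Grade 4, now improved | Met on the literal wording | Already discontinued | No practical conflict |
| Grade 2 hemorrhage, unresolved | Met if non-heme includes bleeding | Held until resolution | Differ on that reading |
| Grade 3-4 hemorrhage, now improved | Met if non-heme includes bleeding | Already discontinued | No practical conflict |

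Size of the gap after grade 3: 2 − 1 = 1 grade if Section 6.2 means ≤1, and 2 − 0 = 2 grades if <1 is literal. The gap is therefore at least one grade.

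One row differs under every reading of the symbols and terms: grade 3 improved to grade 2. The intolerable grade 2 and hemorrhage rows depend on how the Day 29 line is read, and the documents do not define non-heme.

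**The case against.** The strongest reply is that the two rules can both be obeyed. The Day 29 line says what must be true before Cycle 2. It does not say that meeting it lifts a Section 6.2 interruption. A grade 2 ceiling also fits the rule that tolerable grade 2 continues, and it still stops dispensing when a grade 3 toxicity is first found at Day 29. Sections 5 and 6.3 already send the reader to Section 6, and Appendix A Section 5.1 presents the checklists as an aid to complete data capture.

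Most of this stands. A reader might infer a flat contradiction that no site could satisfy; the documents do not support that, because applying the stricter rule satisfies both. What remains is that the line states its own, looser number with no reference to Section 6.2, while the platelet line beside it does refer to its rule. Section 5.1.2 also sends sites to the checklist, which has an investigator signature line.

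A reader might also infer that half of treatment is at stake. Days 29 to 56 are 56 − 29 + 1 = 28 of 56 planned daily doses, and the calendar row "AE/SAE assessment" has no entry between Day 29 and Day 56, a gap of 56 − 29 = 27 days. With the ±2 and ±5 day windows the gap runs from 51 − 31 = 20 to 61 − 27 = 34 days. These figures describe the schedule for every patient and are not an effect of this line. Section 6 collects adverse events throughout, and Section 5.3 allows treatment to stop at any time for an unacceptable event.

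**Conclusion.** The point holds as a mismatch between sections that should be corrected. Section 5.1.2 and Appendix C state a recovery threshold at least one grade looser than Section 6.2 after a related non-hematologic grade 3 toxicity, and they do not mention the separate hemorrhage rule. A site relying on the checklist could dispense Cycle 2 drug to a patient whom Section 6.2 still holds.

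The effect is small. It needs a related grade 3 toxicity that has improved to grade 2 by Day 29, at a site that follows the checklist without Section 6.2. Section 6.1 reports little toxicity with quercetin, so few patients are likely to be affected, but the documents give no basis for a count. Power, alpha and the stopping rules do not change.

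The conclusion does not depend on whether the sign in Section 6.2 is < or ≤. It does assume that Section 6.2 is the intended rule, as the references in Sections 5 and 6.3 indicate. If the sponsor meant grade 2, Section 6.2 is the text to amend.

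**What to change.** In Section 5.1.2 and in the Appendix C Cycle 2 checklist, delete the grade 2 threshold and write:

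*Any toxicity for which isoquercetin was held or interrupted must meet the criteria to resume in section 6.2 (including the hemorrhage rule) before Cycle 2 drug is dispensed.*

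The platelet line stays as it is and keeps thrombocytopenia under Section 6.3. A grade 3 toxicity first found on Day 29 remains covered, because Section 6.2 interrupts drug at that point.

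It is better not to restate the grades in the Day 29 line. Wording that lets tolerable grade 2 continue, or allows re-treatment after a recovered grade 3, would clash with the hemorrhage rule if a site counted bleeding as non-heme.

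The cost is one line of wording in two places, with no change to visits, data collection or sample size.
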